Suicide has been described as "a permanent solution to a temporary problem" (3), reflecting the view that suicide is the result of poor decision making. The strongest biological finding in suicide research is the association with reduced serotonergic neurotransmission, particularly within the ventromedial prefrontal cortex (VMPFC) (4). This deficit in serotonergic neurotransmission is thought to impair cognition, predisposing patients to become more impulsive, rigid in their thinking, and poorer decision makers. Decisions during depressed states are tainted by negative affect and distorted negative cognitions (5). However, suicide has been associated with cognitive impairments that go beyond those of depression. Asymptomatic patients with a history of suicide attempts exhibit significant cognitive deficits suggestive of generalized prefrontal cortex (PFC) dysfunction (6, 7), and corollary disruptions in risk assessment (8). Poor inhibition is found in suicide attempters when compared with patients with only suicidal ideation (9), and greater cognitive impairments are found in depressed patients with suicidal ideation compared to those without it (10). It is possible that cognitive deficits may be specific to suicidal behavior rather than to any comorbid or specific psychiatric diagnosis because this observation holds true for suicidal patients with depression, bipolar disorder, and even temporal lobe epilepsy. However, most of these studies were performed in symptom-free patients, often months or years after the presence of suicidal ideation or behavior. In a previous report (1) we demonstrated that inability to delay gratification (choosing smaller immediate rewards over larger delayed rewards) is shared by both recent suicide attempters and depressed patients with suicidal ideation. On a follow up assessment, 5-10 days after the suicide attempt, reduction of suicidal ideation and intent was correlated with decreased symptoms of depression

and recovery of delayed gratification impairments (1). These data are congruent with the hypothesis that stressful situations in combination with a biological and psychological predisposition may create a critical climate of overwhelming psychological pain in an individual who chooses an impulsive escapist strategy to terminate his/her own life discounting all future outcomes (11). However, the underlying neural mechanisms remain unknown and therefore not amenable to therapeutic interventions.

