Repetitive TMS (rTMS) will be delivered to the left PFC, defined as a location 6 cm (cm) anterior to the right hand motor thumb area. A research nurse will deliver the treatments. rTMS will be delivered with a figure-eight coil at 120% motor threshold, 10 Hertz (Hz), 5 s (s) train duration, 26 s intertrain interval for 50 min (6000 pulses) 3 times daily for 3 days (total 9 sessions, 54,000 stimuli). Similar parameters were previously used in a population of acutely suicidal veterans and military patients with even more severe comorbidity than our proposed sample because of comorbid posttraumatic stress disorder and traumatic brain injury without significant adverse effects (13). Variations will be allowed in the dosing schedule to accommodate the patient's inpatient schedule and staffing needs, with at least 1 hour between sessions. Treatments will be done on consecutive days, with the goal to deliver 9 sessions over three days. Adverse events will be assessed at each treatment session as well as daily. Prior to and then immediately after each rTMS session, subjects will complete visual analog scales (VAS) on a laptop computer located next to the rTMS chair. Patients will wear earplugs and will not be allowed to sleep. Counseling or other conversation during treatment will be discouraged.

Sham treatment

Parameters for sham rTMS are identical to those for active stimulation except that aluminum plate blocks the propagation of a magnetic field. The sound and physical sensation is the same as with the active coil while been biologically inactive.

Assessments

Trained and blinded study staff (raters) will administer assessments as described in Table 2. Additionally, menstrual cycle phase will be characterized for female subjects (i.e. date of last period, regularity of menstrual cycle).

PI: [name]

Table 2. Assessments administration schedule during the proposed study									
Task	Intake &	Pre rTMS	Post rTMS	Post	Before	3 & 6 month			
	Pre rTMS	Session 1	Session 3	rTMS	Discharge	follow-up			
	Session 1	(day 2 & 3)	(day 1 & 2)	Session 3					
	(day 1)			(day 3)					
Informed Consent Capacity	X								
Checklist									
Informed consent	X								
Demographic Data Form	X								
Columbia Suicide Severity Rating	X				X	X			
Scale (C- SSRS)									
Hamilton Rating Scale for	X			X	X	X			
Depression (HAM-D)									
Hamilton Anxiety Rating Scale	X			X	X	X			
(HAM-A)									
Beck Scale for Suicidal Ideation	X			X	X	X			
Beck Hopelessness Scale	X	X	X	X	X	X			

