Delay discounting task	X	X	X	X	X	X			
N back test	X	X	X	X	X	X			
Stroop Test	X	X	X	X	X	X			
Young Mania Rating Scale	X	X	X	X	X	X			
DKEFS Verbal Fluency Test	X	X	X	X	X	X			
Pressure pain threshold	X	X	X	X	X	X			
Sham validating measure				X					
Trail making A and B	X	X	X	X	X	X			
Visual Analog Scales**	X	X	X	X	X	X			
MINI International	X								
Neuropsychiatric Interview (MINI)									
Randomization	X								

^{**} This assessment will be collected 3 times per day pre and post rTMS.

Safety Assessments

Research staff will use the MedDRA System Organ Class (SOC) and preferred term (PT) to document adverse events, which will be assessed at each treatment, and at follow-up visits.

This protocol will not modify patient care and our visits will not interfere with regular clinical care, except in the case of imminent danger to the patient or others in which appropriate measures will be taken, like contacting the primary treatment team and placing the patient on 1:1 observation until evaluation by the primary team.

STUDY POPULATION

Participant recruitment will occur at the inpatient units at the Psychiatric Research Institute (PRI). Target sample size is 20, which will be randomized into active or sham groups (1:1). Considering 40% attrition rate we plan to recruit 28 participants.

Recruitment: Recruitment will be facilitated by the PI's role of PRI inpatient attending physician. The success of this proposal depends heavily on the ability to recruit patients very soon after hospitalization for

PI: [name]

suicide ideation or behavior.

All participants will be compensated \$40 for their participation in each of the 3 rTMS sessions of the active phase of the study and the 2 follow-up sessions. Participants can earn a total of \$200 for completing the entire study, including both follow up visits.

Inclusion Criteria

- a) Age 18-60 years, of all races and ethnicities;
- b) Admitted voluntarily to the adult psychiatric inpatient at PRI;
- c) Suffering from a current depressive episode as defined by the DSM-V
- d) Currently have diagnoses of major depressive disorder
- e) Reason for hospitalization should be a recent suicide attempt or suicidal ideation
- f) Current severe suicidal ideation defined by a score >7 in the Beck Scale for Suicidal Ideation
- g) Must pass the TMS safety checklist (TASS)
- h) Women of childbearing age must have a negative result on a pregnancy test
- i) Ability to read, write and speak English.

Exclusion Criteria

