The Principal Investigator will carefully monitor study procedures to protect the safety of research subjects, the quality of the data and the integrity of the study. To protect the identity of research volunteers, contact information will be stored in a separate file and locked cabinet, away from experimental data forms. All study subject material will be assigned a unique identifying code or number. The key to the code will be kept in a locked file in the Study Coordinator's office. Only [name] and designated research staff will have access to the code and information that identifies the subject in this study. All experimental data will be identified using a study code rather than a name, social security number, or other identifying information. All data collection forms will be kept in a locked cabinet in the Psychiatric Research Institute. Computer data records will remain on UAMS maintained password protected network drives.

DATA ANALYSIS

Cognitive tests and questionnaires

Data will be scored and analyzed/summarized according to instructions. Scores will be analyzed via t-tests, analysis of variance (ANOVA) or regression analysis.

PI: [name]

The primary outcome (impulsive choice measured by delay discounting) will be analyzed using an MMRM (mixed model repeated measures) approach based on a modified intent-to-treat (mITT) population. The mITT population will be defined as randomized subjects who started at least one treatment. Participants from the mITT population who are included in the MMRM model will also require both a baseline and at least one post- baseline SSI score. The model will include as the dependent variable change from baseline in delay discounting indifference point (K) at each post-baseline visit during the acute phase. Independent variables in the MMRM model will include treatment, visit, treatment-by-visit interaction, delay discounting at baseline, gender, age at baseline and diagnosis. Visits (Days 0, 1, 2, 3) will be treated as a categorical variable. Unstructured variance-covariance structure will be used. This same analysis will also be repeated on the completers' population, defined as subjects who completed 3 days of treatment with the scheduled maximum 6000 pulses per session.

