Analyses of VAS data will be conducted using a similar MMRM approach. Each VAS item will be analyzed separately. For the suicide, mood and anxiety items, the model included as the dependent variable change scores from pre-session 1 (session prior to intervention) to each post-session (sessions 1-9) during the acute phase. Independent variables included treatment, session, treatment-by-session interaction, VAS score at pre-session 1, gender, age at baseline, and diagnosis. Painfulness questions collected only at each post-session will be analyzed using an MMRM approach with post-session scores as the dependent variable. Independent variables will remain the same.

Descriptive analyses will be performed to compare baseline data between treatment groups. Categorical variables will be evaluated using Fisher's exact test. Continuous variables will be analyzed with Wilcoxon's rank sum test.

Safety data will be summarized overall and by treatment groups. Fisher's exact test will be used to compare the number of subjects between groups who experienced any adverse events. Length of hospital stay will be compared using Wilcoxon Rank Sum test. Time to re-admission will be analyzed with log-rank test.

The Stroop Test, N-Back scores and pain pressure threshold will be added as covariates in final analysis. Other secondary efficacy outcomes (HRSD, MADRS, CAPS and SSI) for the extended safety phase will be analyzed with MMRM model. The model will include the change from baseline at each follow-up visit as the dependent variable. Independent variables include treatment, visit, treatment-by-visit interaction and base- line score.

We will use repeated measures ANOVA (with appropriate statistical corrections) to compare measures obtained at baseline to those collected 3 & 6 months after all experimental treatment ends. This analysis will address long-term effects of rTMS experimental treatment on suicidal ideation.

The integrity of the blind will be analyzed by tables and Fisher's exact test.

All statistical analyses will be performed in R version 2.14.0. Because this is an early phase study, no adjustments will be made for multiple comparisons, and a *P*-value of 0.05 will be considered to be statistically significant.

Power estimation

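### The delay discounting MMRM admits subjects on a post-baseline SSI score rather than a post-baseline K, so some early leavers with valid K data are excluded

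*Combined protocol and SAP*

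**What the plan says.** The Data Analysis section labels impulsive choice, measured by delay discounting, as the primary outcome. The dependent variable is "change from baseline in delay discounting indifference point (K) at each post-baseline visit during the acute phase". The covariates include "delay discounting at baseline, gender, age at baseline and diagnosis". The modified intent-to-treat population is everyone randomised who started at least one treatment. A further condition then applies to entry into the model: subjects "will also require both a baseline and at least one post- baseline SSI score". No condition on K is written.

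The same section lists SSI among secondary outcomes: "Other secondary efficacy outcomes (HRSD, MADRS, CAPS and SSI) for the extended safety phase". The abbreviation is not expanded anywhere. The Table 1 row for the "Beck Scale for Suicidal Ideation" cites a reference whose title names the Scale for Suicide Ideation, so that instrument is the natural reading.

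In Table 2 the row "Delay discounting task" is marked in every column. The Beck scale row is marked at intake, after session 3 on day 3, before discharge, and at 3 and 6 months. It is blank before session 1 on days 2 and 3, and after session 3 on days 1 and 2.

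On attrition, the Study Population section says: "Considering 40% attrition rate we plan to recruit 28 participants".

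**The concern.** An MMRM uses the partial data of early leavers only if those subjects are in the model. Here admission depends on a different instrument, first repeated two days after K is first repeated. Whether a subject has a post-baseline Beck score is known only after randomisation, and it says nothing about whether K was measured. The rule therefore discards valid outcome data from some treated subjects and moves the modified intent-to-treat analysis towards the completers' analysis, which the plan lists separately.

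Two things could follow: a loss of precision in a very small trial and, under particular dropout patterns, bias in the treatment difference. Leaving during treatment is foreseen. The Safety Assessments section and the paragraphs on mood effects list reasons for withdrawal from the study, and Table 2 has no early-termination visit.

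**Working it through.** **Who is excluded.** Counting post-baseline scores in Table 2 by the last assessment attended, with nothing collected later:

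| Last assessment attended | K | Beck | Rule as written | Rule based on K |
|---|---|---|---|---|
| Day 1, before session 1 (baseline) | 0 | 0 | out | out |
| Day 1, after session 3 | 1 | 0 | out | in |
| Day 2, before session 1 | 2 | 0 | out | in |
| Day 2, after session 3 | 3 | 0 | out | in |
| Day 3, before session 1 | 4 | 0 | out | in |
| Day 3, after session 3 | 5 | 1 | in | in |

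The two rules differ in four rows. Up to four K assessments are lost per subject. The model has one visit per day (Days 0 to 3), and the plan does not say which of two same-day scores is used; taking the end-of-day score, one or two modelled values are lost. The written rule is not confined to the acute phase, so a Beck score at discharge or follow-up readmits the subject.

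**How many.** The plan's figures give 28 - 20 = 8 or 0.40 x 28 = 11.2 leavers. The share falling in this window is not stated. From 0% to 100% of 11.2, the count runs from 0 to 11.2. If a quarter fell there (an assumption), it is 0.25 x 8 = 2.0 to 0.25 x 11.2 = 2.8. Using 28 as denominator also assumes that attrition follows randomisation. The Study Population section says the target of 20 is what is randomised, and entry criteria are applied after consent, so some attrition may come earlier.

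**Bias.** This was simulated with raw K at baseline and days 1-3, no true effect, and adjustment for baseline K. In the active arm the chance of leaving rises with K change (logistic slope 0.5 or 1 per SD of change); in the sham arm leaving is random. Leaving is split between after day 1 and after day 2, and no leaver gives a later Beck score. All of these are assumptions. Day 3 bias in favour of active, in SD of raw K, at 10% / 20% loss:

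| Correlation of raw K | Slope 0.5 | Slope 1 |
|---|---|---|
| Equal, 0.5 | 0.012 / 0.026 | 0.025 / 0.049 |
| Equal, 0.7 | 0.014 / 0.028 | 0.024 / 0.050 |
| Decaying, 0.5 per step | 0.017 / 0.030 | 0.028 / 0.056 |
| Decaying, 0.7 per step | 0.023 / 0.045 | 0.041 / 0.082 |

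On days 1-2 the same scenarios give about 0.02-0.06 at 10% loss and 0.05-0.12 at 20%. These matter because the plan fits treatment by visit and names no single day as its contrast. If half the leavers give a later Beck score (equal correlation), day 3 bias falls to 0.005-0.012 and 0.012-0.023. With random leaving, or the same mechanism in both arms, or all observed K kept, day 3 bias is within 0.002 of zero.

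For scale, the Power estimation section gives (0.122 - 0.099)/SD = 0.23, so SD = 0.023/0.23 = 0.10. A bias of 0.12 SD is then 0.012 in K, against the plan's meaningful difference of 0.023.

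**Precision under random leaving.** On day 3 the leavers have no K, so excluding them loses only what their earlier values would contribute. Simulated standard errors (14 per arm, baseline K plus gender, age and diagnosis, the last three taken as unrelated to K), rule as written versus K kept:

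- correlation 0.5: 0.373 v 0.372 (2 deleted), 0.383 v 0.381 (3), 0.418 v 0.416 (6);
- correlation 0.7: 0.306 v 0.305 (2), 0.317 v 0.314 (3), 0.344 v 0.338 (6).

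The increase is 1% or less for 2-3 deleted and 0.5-1.8% for 6. On day 1 every deleted subject had an observed K. With equal variances and balanced loss the ratio is sqrt(28/(28 - m)): sqrt(28/26) = 1.04, sqrt(28/25) = 1.06 and sqrt(28/22) = 1.13.

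**The case against.** The strongest reply is that few subjects, perhaps none, will be caught. All are inpatients, so one who stops stimulation need not have left hospital, and a discharge Beck score would satisfy the rule. That is fair, and it limits the numbers. But the plan does not say that withdrawn subjects are still assessed. The paragraphs on mood effects promise daily checks for worsening ideation but name no instrument, and Table 2 shows no Beck scale between intake and the end of day 3.

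A second reply is that SSI is simply a wrong label, perhaps carried over from another plan: the secondary list also names MADRS and CAPS, which Table 2 does not schedule. That is plausible. Even so, the text as written decides who enters the model, and changing it once the leavers are known would be a post hoc change to the analysis set.

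A reader might infer that the rule biases the estimated effect of rTMS, because subjects withdrawn for worsening depression would also have worse discounting. The documents do not support that. The Background reports that "reduction of suicidal ideation and intent was correlated with decreased symptoms of depression" and also with recovery of discounting. Both are tied to suicidal ideation; no direct link between depression and discounting is stated, no withdrawal rule is defined by K, and nothing shows that leaving would differ by arm.

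Finally, the protocol elsewhere names safety as the primary objective and endpoint. The rule does not touch the safety analysis, which lowers the stakes further.

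**Conclusion.** The entry condition is wrong as written: it selects subjects for a delay discounting model by a different scale on a sparser schedule. It excludes a subject only if three things hold: SSI means the Beck scale, the subject leaves between the first post-baseline K and the day 3 Beck scale, and no later Beck score is given.

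The size is uncertain but small. Under assumed active-arm-only, K-related leaving with no later Beck score, the largest bias is about 0.12 SD of raw K (days 1-2, 20% loss). That is well below the simulated day 3 standard error of about 0.31-0.42 SD. Under random leaving there is no bias. The precision cost is slight at day 3 but not negligible at day 1 if several subjects are deleted. All counts out of 28 depend on attrition falling after randomisation. The textual mismatch is certain; the bias is only possible. Severity: minor.

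**What to change.** In the Data Analysis section, replace the SSI condition with: *a baseline and at least one post-baseline delay discounting score*. Add that K scores collected before a subject leaves are kept in the model. Where SSI remains in the list of secondary outcomes, spell out which instrument is meant. The cost is one or two sentences of analysis text, with no new data and no change to procedures, and the change should be made before unblinding.

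### Read as unstructured, the nine-session VAS model needs 45 covariance parameters from 20 to 28 patients, and its uncorrected joint treatment-by-session test rejects a true null about 24% to 37% of the time

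*Combined protocol and SAP*

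**What the plan says.** The Data Analysis section of the combined protocol and SAP first describes the mixed model for delay discounting (K). Its covariance statement is: "Unstructured variance-covariance structure will be used". The next paragraph turns to the VAS: "Analyses of VAS data will be conducted using a similar MMRM approach", with each item modelled separately. For the suicide, mood and anxiety items the outcome is "change scores from pre-session 1 (session prior to intervention) to each post-session (sessions 1-9) during the acute phase". The model terms are given as: "Independent variables included treatment, session, treatment-by-session interaction, VAS score at pre-session 1, gender, age at baseline, and diagnosis".

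The section states no covariance structure specific to the VAS. It also gives no choice between REML and ML, no denominator degrees-of-freedom method, no small-sample correction and no fallback if a fit fails. The software statement, "All statistical analyses will be performed in R version 2.14.0", does not settle any of these. Tests are at 0.05 without multiplicity adjustment.

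Under Study Population the target is 20 patients allocated 1:1, and "Considering 40% attrition rate we plan to recruit 28 participants". For the K model, "The mITT population will be defined as randomized subjects who started at least one treatment", so if the VAS models use the same population, anything from about 20 to 28 patients could enter, some with missing sessions.

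**The concern.** An unstructured matrix is a reasonable default when patients greatly outnumber the distinct variances and covariances. Here nine occasions would be fitted to 20 to 28 patients. A Wald-type test that treats so poorly estimated a matrix as known, or nearly known, rejects too often, and the more contrasts it tests jointly the worse this becomes.

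In Table 2 the Beck ideation scale is given at intake, after the last session on day 3, before discharge and at follow-up, and the C-SSRS less often. VAS suicidality is the only ideation measure taken around every session, so its treatment-by-session term is where a difference in time course during treatment would appear. A false positive there could be read as rapid benefit. Each item modelled this way carries the same inflated error, and nothing adjusts across items.

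**Working it through.** The plan gives no error rate or power for the VAS models beyond the nominal 0.05, so there is no planned figure to reproduce.

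**Inputs.** Nine occasions, two arms, and n=20 (target) or n=28 (recruited), all from the plan. I also take n=16, because 28 × (1 − 0.40) = 16.8. Assumptions: unstructured covariance carried over, complete data, normal errors, REML, no small-sample correction, and one parameter for each of the four covariates.

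**Parameter count.** Covariance: 9 × 10 / 2 = 45. Mean: 2 × 9 + 4 = 22. Residual df = 9n − 22.

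**Distribution of the test.** The interaction is 8 contrasts among sessions compared between arms. The four covariates are constant over time and not crossed with session, so they shift all nine scores equally and cancel from these contrasts. Error df is therefore n − 2, with or without the covariates. The Wald statistic is Hotelling's T² on 8 contrasts, and T²(n−9) / [8(n−2)] follows F(8, n−9). If T²/8 is compared with a cut-off c, the true rejection rate is

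P{ F(8, n−9) > c × (n−9)/(n−2) }.

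| n | Reference used | c | c × (n−9)/(n−2) | True rate |
|---|---|---|---|---|
| 20 | F(8, 158), residual | 1.997 | 1.997 × 11/18 = 1.221 | 37.0% |
| 20 | F(8, 18), n−2 | 2.510 | 2.510 × 11/18 = 1.534 | 25.0% |
| 28 | F(8, 230), residual | 1.979 | 1.979 × 19/26 = 1.446 | 24.1% |
| 28 | F(8, 26), n−2 | 2.321 | 2.321 × 19/26 = 1.696 | 16.4% |
| 16 | F(8, 122), residual | 2.015 | 2.015 × 7/14 = 1.008 | 50.3% |
| 16 | F(8, 14), n−2 | 2.699 | 2.699 × 7/14 = 1.349 | 35.3% |

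A chi-square(8) reference gives 38.7%, 25.2% and 52.3% at n = 20, 28 and 16. The cut-off that restores 5% is (18/11) × 2.948 = 4.82 at n=20 and (26/19) × 2.477 = 3.39 at n=28. Moving to n−2 df at n=20 raises the cut-off only from 2.00 to 2.51, so changing the df is not enough.

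**Simulation check.** REML unstructured fits with four time-constant covariates and a true common correlation of 0.7 gave 35.1% (residual df) and 23.5% (n−2) at n=20 with complete data (1,500 fits). At n=16 they gave 46.5% and 29.3% (600 fits), 4 to 6 points below the exact values. With 20% dropping out during treatment at n=20, the rate was 40% to 54% depending on the reference; with 40% dropping out at n=28, it was 37% to 48%. The dropout fractions and correlation are assumptions.

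**Where the inflation does not reach.**
- One active-versus-sham contrast at one session, n−2 error df and residual-df cut-off: P(|t(18)| > 1.975) = 6.4% at n=20 and P(|t(26)| > 1.970) = 6.0% at n=28.
- K model read as three post-baseline visits (2 contrasts, 6 covariance parameters, residual df 3n − 10): at n=20, 3.183 × 17/18 = 3.006 and P{F(2, 17) > 3.006} = 7.6%; at n=28, 3.120 × 25/26 = 3.000 and P{F(2, 25) > 3.000} = 6.8%.

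**The case against.** The main objection is that the premise is inferred. The plan says the VAS approach is similar to the K model, not identical, and names no VAS covariance. That is fair, and the error rates are conditional on the carry-over. But unstructured is the only structure the plan offers, and if something else was meant it still has to be written down.

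Second, the plan lists the interaction as a model term without naming the 8-df joint test as the decision test. This also stands, and it limits the point to that test. A reader might infer that every test from these models is badly inflated; single-session contrasts at about 6% show otherwise.

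Three other stronger readings should be set aside:
- A reader might charge the four covariates against the error df and reach about 50% with 20 complete patients. They cancel from the session contrasts, so 20 complete patients give 25% to 39% depending on the reference. About 50% needs some 16 patients analysed, or dropout.
- A reader might treat VAS suicidality as the trial's test of faster resolution of ideation. The documents never link the two: Hypothesis 3.1 names the Beck scale, the stated primary outcomes are safety in one place and delay discounting in another, and no VAS item is declared confirmatory.
- A reader might expect missed sessions to make non-convergence likely. This was not shown: at n=20 with 30% dropout, 499 of 500 simulated fits finished. Another fitting routine could behave differently, which is a reason to state a fallback but not evidence of failure.

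Calling the study early phase explains the lack of multiplicity adjustment. It does not justify a nominal 5% test with several times that error.

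**Conclusion.** The point holds in a limited form. If the unstructured covariance is carried to nine sessions and no small-sample correction is used, the joint treatment-by-session test for each VAS item has a true error of about 37% at n=20 and 24% at n=28 with residual df, or 25% and 16% with n−2 df. At 16 analysed patients it is about 50% with residual df. Even the mildest of these, 16.4%, is more than three times nominal. The figures are exact for complete, normal data; in the simulations, dropout raised them. They do not extend to single-session contrasts, and the three-visit K model is only mildly affected. Because the VAS is a secondary, exploratory outcome, this should be corrected but does not threaten the trial's main conclusions.

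**What to change.** State the VAS model in full, choosing one of two forms:
- average the post-session scores within each day, giving 3 visits and 3 × 4 / 2 = 6 covariance parameters; or
- keep nine sessions with a random subject intercept and first-order autoregressive errors, which has 3 covariance parameters (two variances and one autocorrelation).

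In either case specify REML and Kenward-Roger inference, name the routine that provides it in the stated software, and give an ordered fallback if a fit fails. Apply the same small-sample correction to the K model.

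If the unstructured matrix is kept for nine sessions, the statistic must be rescaled as well as given new df, by Kenward-Roger or a Hotelling-type reference. The exact Hotelling reference returns 5.0% with complete data.

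A robust standard error used to check the assumed correlation also needs a small-sample correction. In a simulation of 3,000 runs with correlation 0.7 and residual df, an uncorrected one rejected 42% at n=20 and 29% at n=28, worse than the unstructured fit in the same runs (37% and 25%).

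The cost is a few lines of SAP text. The price is loss of within-day detail under the first form, or reliance on an assumed correlation pattern under the second. The plan breaks the blind only after analysis, so the change can be made without knowledge of treatment.
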